Allogeneic HB-adMSCs to provide immune support against COVID-19.

Study Endpoints

Primary endpoints:

- Incidence of hospitalization for COVID-19.
- Incidence of symptoms associated with COVID-19.

Secondary endpoints:

- Absence of upper/lower respiratory infections (with hospitalization criteria) up to 3 months post infusions.
- Change from baseline in leukocyte differential
- Change from baseline in C-Reactive Protein
- Change from baseline in TNF-alpha
- Change from baseline in IL-6
- Change from baseline in IL-10
- Clinically significant changes in laboratory values, vital signs, weight, X-rays, ECG, and physical examination results.
- Incidence of AEs (AEs) and serious AEs (SAEs) related to the drug

Investigational Plan

This Phase 2, randomized, double-blind, single center, efficacy and safety study, is designed to evaluate allogeneic HB-adMSCs to provide immune support against COVID-19 in subjects classified as high risk. 'High risk', according to CDC at the time of protocol development, includes subjects age 65 or older, as well as subjects in high exposure environments such as healthcare professionals and law enforcement, or individuals with preexisting conditions, including but not limited to cardiopathies, diabetes mellitus, cancer, COPD, asthma or any other systemic autoimmune disease. The study will have 4 arms:

Arm 1 (allogeneic HB-adMSCs 200MM)

Subjects assigned to this arm will receive HB-adMSCs during the whole duration of the study.

Arm 2 (allogeneic HB-adMSCs 100MM)

Subjects assigned to this arm will receive HB-adMSCs during the whole duration of the study.

Arm 3 (allogeneic HB-adMSCs 50MM)

Subjects assigned to this arm will receive HB-adMSCs during the whole duration of the study.

Arm 4 (Placebo)

Subjects assigned to this arm will receive placebo injections throughout the entire duration of the study.

The screening period, up to 45 days long for each patient, will be used to assess eligibility. At baseline (Week 0), approximately 53 patients who are eligible will be randomized in a 3:1 ratio

Allogeneic HB-adMSCs to provide immune support against COVID-19.

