to the HB-adMSCs and Placebo groups, respectively. Safety assessments will be ongoing. Complete Blood Count, Comprehensive Metabolic Profile and Coagulation Panel will screen for hepatotoxicity, renal failure or alterations in the coagulation cascade that might entail a safety concern for the individual. Efficacy assessments will include PHQ-9, SF-36, TNF-a, IL-6, IL-10, and CRP.

The trial is designed to be conducted over 3 periods or phases:

- **Phase 1** (screening): Our screening process starts with a telephone call to provide a general overview of the study and discuss eligibility requirements. The study patient will receive the informed consent document by e-mail or in the pre-paid envelope provided. If, after reviewing this consent the study patient is still interested in participating in the study, he/she will need to sign and return the consent form to Hope Biosciences Stem Cell Research Foundation. This process can take up to 45 days.
- **Phase 2** (Treatments): Includes Infusion 1 (Week 0), Infusion 2 (Week 2), Infusion 3 (Week 6), Infusion 4 (Week 10) and Infusion 5 (Week 14). Subjects will be monitored at the clinical site for 1 hours following HB-adMSCs administration.
- **Phase 3** (follow-up): Includes Follow Up Week 18, 22 and End of Study at Week 26.

Selection and Withdrawal of Patients

Inclusion Criteria

Inclusion Criteria:

1. Men, and women 18 years of age or older
2. Participant works in a capacity that is characterized as high-risk or very high-risk
 - a. High-Risk Exposure jobs are those with high potential for exposure to known or suspected sources of COVID-19.
 - First responders, health care delivery and support staff (e.g., law enforcement, fire fighters, paramedics, doctors, nurses, and other hospital staff who must enter patients' rooms) exposed to individuals potentially having COVID-19.
 - Mortuary workers involved in preparing (e.g., for burial or cremation) the bodies of people who are known to have, or suspected of having, COVID-19 at the time of their death
 - b. Very High-Risk Exposure jobs are those with high potential for exposure to known or suspected sources of COVID-19 during specific medical, postmortem or laboratory procedures.
 - Health care workers (e.g., doctors, nurses, dentists, paramedics, emergency medical technicians) performing aerosol-generating procedures (e.g., intubation, cough induction

Allogeneic HB-adMSCs to provide immune support against COVID-19.

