- procedures, bronchoscopies, some dental procedures and exams or invasive specimen collection) on known or suspected COVID-19 patients
- Health care or laboratory personnel collecting or handling specimens from known or suspected COVID-19 patients (e.g., manipulating cultures from known or suspected COVID-19 patients)
 - Morgue workers performing autopsies, which generally involve aerosol-generating procedures, on the bodies of people who are known to have, or suspected of having, COVID-19 at the time of their death
3. No signs or symptoms of infection, including but not limited to, body temperature >100 F and pulse rate > 100 BPM.
 4. Subject provides written informed consent prior to initiation of any study procedures.
 5. Agrees to the collection of venous blood per protocol.
 6. Agrees to conformational testing for SARS-CoV-2 before end of study.

Exclusion Criteria

1. Women who are pregnant or lactating, or those who are not pregnant but do not take effective contraceptive measures
2. Patients who are participating in other clinical trials or have intake of investigational drug within the previous 30 days;
3. Inability to provide informed consent or to comply with test requirements;
4. Any medical disease or condition that, in the opinion of the site PI or sub-investigator, precludes study participation. Including acute, subacute, intermittent or chronic medical disease or condition that would place the subject at an unacceptable risk of injury, render the subject unable to meet the requirements of the protocol, or may interfere with the evaluation of responses or the subject's successful completion of this trial.
5. Patients who have received a stem cell treatment within one year.
6. Receipt of any other SARS-CoV-2 or other experimental coronavirus vaccine at any time prior to or during the study.
7. Patient currently or recently symptomatic for COVID-19 or anyone with COVID-19 associated symptoms within the past 30-days

Withdrawal, Removal, and Replacement of Patients

Patients will be considered to have completed the study if they complete treatment and assessments through Week 26. A patient's investigational treatment should be discontinued if any of the following situations occurs:

- The Investigator believes that for safety reasons, it is in the best interest of the patient to stop treatment.
- The patient is non-compliant with the study visit schedule or other protocol requirements.

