Unblinding of patient and researcher will occur in the case of adverse event suspected to be related to the investigational product, per the medical monitor and DSMB.

Regulatory authorities and/or the IRB may request the unblinding of data from one or more patients at any time.

Prior and concomitant conditions

The investigators should document all prior significant medical history. Additional conditions present at the time when informed consent is given and up to the time of first infusion (Week 0) are to be regarded as concomitant conditions. Illnesses first occurring or detected during the study and/or worsening of a concomitant condition during the study should be documented as AEs in the CRF.

Prior and concomitant medications

All medications, including over-the-counter treatments and preventative vaccines taken by the patient during the study, including those treatments initiated prior to the start of the study, must be recorded in the CRF. The entry must include the dose, regimen, route, indication, and dates of use.

Study Procedures

Table 2 outlines the timing of procedures, and assessments to be performed throughout the study.

Table 2. Schedule of Assessments

Visit Number	1	2	3	4	5	6	7	8	9
Weeks	N/A	Week 0	Week 2	Week 6	Week 10	Week 14	Week 18	Week 22	Week 26
Visit Name	Screening (Phone call)	Infusion-1 /Baseline	Infusion 2	Infusion 3	Infusion 4	Infusion 5	Follow Up	Follow Up	EOS
Window Period	Up to 45 days	±4 days	±4 days	±4 days	±4 days	±4 days	±4 days	±3 days	±3 days
STUDY PROCEDURES									
Informed Consent	X	X							
Inclusion and Exclusion Criteria	X	X							
Pre-infusion assessment		X	X	X	X	X			
Review of Medical History	X	X	X	X	X	X	X	X	X
Concomitant Medication Review	X	X	X	X	X	X	X	X	X

Allogeneic HB-adMSCs to provide immune support against COVID-19.

Vital Signs		X	X	X	X	X	X	X	X
Weight and Height ¹		X	X	X	X	X	X	X	X
Physical Examination		X	X	X	X	X	X	X	X
SF-36 Questionnaire		X	X	X	X	X	X	X	X
PHQ-9		X	X	X	X	X	X	X	X
Rapid antibody COVID-19		X							X
CBC with differential		X		X		X			X
Chemistry		X		X		X			X
Coagulation Panel		X		X		X			X
CRP		X		X		X			X
IL-6		X		X		X			X
IL-10		X		X		X			X
TNF alpha		X		X		X			X
HB-adMSCs Administration		X	X	X	X	X			
24-hour telephone encounter		X	X	X	X	X			
Adverse Event Monitoring		X	X	X	X	X	X	X	X
1. Height will only be measured at baseline									

Informed Consent (ICF)

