A complete physical examination (head, eyes, ears, nose, throat, heart, lungs, abdomen, skin, cervical and axillary lymph nodes, neurological, and musculoskeletal systems) will be performed

Allogeneic HB-adMSCs to provide immune support against COVID-19.

at baseline visit. In addition, medical history (including smoking history) will be recorded at baseline.

A limited physical examination to verify continued patient eligibility and to follow up any change in medical history will be performed at the visits indicated in the schedule of assessments. Symptom-driven physical examinations will be performed as clinically indicated at any study visit. All changes not present at baseline or described in the past medical history and identified as clinically noteworthy will be recorded as AEs.

Clinical Laboratory Parameters

The Investigator must review all laboratory reports and document the review. Any laboratory test result or change considered by the Investigator to be clinically significant should be considered an AE and recorded in the AE CRF. Clinically significant abnormal values occurring during the study will be followed until repeat test results return to normal, stabilize, or are no longer clinically significant.

Laboratory tests to be performed during the study:

Complete Blood Count with Differential	IL-6
Chemistry	IL-10
Coagulation study (PTT/PT/INR)	Tumor Necrosis Factor alpha
C Reactive Protein	Rapid Antibody Test for COVID-19

Adverse Events

An AE is any symptom, physical sign or disease that either emerges during the study or, if present at screening, worsens during the study, regardless of the suspected cause of the event. All medical and psychiatric conditions (except those related to the indication under study) present at screening will be documented in the medical history CRF. Changes in these conditions and new symptoms, physical signs, or diseases should be noted on the AE CRF during the rest of the study.

Clinically significant laboratory abnormalities should also be recorded as AEs. Surgical procedures that were planned before the patient enrolled in the study are not considered AEs if the conditions were known before study inclusion; the medical condition should be reported in the patient's medical history.

Serious Adverse Events (SAE)

A serious adverse event (SAE) is any AE that is:

Allogeneic HB-adMSCs to provide immune support against COVID-19.

- fatal
- life-threatening
- requires or prolongs hospital stay

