The risks associated with this cellular product are currently unknown and have not been studied in this population, to date. There is a potential risk of increased vulnerability to COVID-19, worsening of the disease, and/or complications from the disease. Although currently not

Allogeneic HB-adMSCs to provide immune support against COVID-19.

observed in HB-adMSCs, risks of infusion with MSCs include infusion-related reactions, thrombogenesis or malignancy.

The types of risk associated with HB-adMSCs are also stated in the Informed Consent Form (See ICF)

Minimization of Risks

Although the risk to subjects participating in the study is anticipated to be minimal, the clinician, at his/her discretion, will not collect data from those individuals for whom collection is judged to pose an unusually high risk of physical or mental harm or discomfort.

Participation in this study poses moderate risk to study personnel related to potential pathogens that may be present in the subject's specimens which are then expanded during the culture process. These risks will be minimized by adherence to the principles of universal precautions and by conducting the planned testing on blood from the subject at screening for particular pathogens of concern.

Personnel should wear appropriate personal protective equipment to avoid contact of the eyes or skin with hazardous materials or products derived from biological sources.

Subjects will be advised to follow current federal guidelines regarding COVID-19 such as the following:

- Use hand sanitizer that contains at least 60% alcohol
- Avoid touching your eyes, nose, and mouth with unwashed hands
- Avoid close contact
- Adhere to social distancing guidelines and maintain at least 6' of distance with others

General procedures for personnel include:

- Hands must be washed with soap and water for at least 20 seconds, if soap and running water are unavailable, an alcohol-based hand rub with at least 60% alcohol will suffice this action. Always wash hands that are visibly soiled.
- Avoid touching their eyes, nose or mouth.
- Healthcare workers will wear:
 - o Gowns
 - o Gloves
 - o Disposable surgical masks.
 - o Eye/face protection (e.g., goggles, face shield)
- Surfaces where subjects have been in contact will be disinfected 70% Isopropyl Alcohol, hydrogen peroxide, or Clorox disinfectant.

Allogeneic HB-adMSCs to provide immune support against COVID-19.

Potential Benefits

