Men, and women, age 65 or older OR high exposure risk individuals (healthcare professionals and law enforcement), OR individuals considered to be high risk due to preexisting conditions.

Safety: all subjects that receive at least one HB-adMSCs infusion will be included in safety analysis

Efficacy: all subjects that receive all 5 infusions of HB-adMSCs will be included in efficacy analysis

Demographic and Baseline Characteristics

Information describing subjects' gender, race/ethnicity, and age will be displayed in tables similar to the ones included below. The number and percent of the total sample population will be calculated for each demographic category.

Demographics	Female		Male		Both Genders	
	N	%	N	%	Total	%
Race/Ethnicity						
White						
Black or African American						
Hispanic or Latino						
Other (Specify)						
Total						

The mean, minimum, and maximum age at enrollment will be determined using standard calculations. The number and percent of total subjects in each age group will be calculated and reported.

Age at Enrollment	
Mean	
Minimum	
Maximum	

Allogeneic HB-adMSCs to provide immune support against COVID-19.

	N	%
18-21 years		
22 – 29 years		
30 - 39 years		
40 - 49 years		
50 - 59 years		
60 – 69 years		
70 – 79 years		
80 – 89 years		
90 – 99 years		
100 – 109 years		
Total	100	100%

Safety Analysis

The number, type, and description of all AEs and SAEs will be recorded and reported. Clinical laboratory values will also be recorded and reported.

Efficacy Analysis

Efficacy will be measured by incidence of hospitalization for COVID-19, incidence of symptoms associated with COVID-19, and severity of symptoms associated with COVID-19. We will also record and reported inflammatory markers and SF-36, PHQ-9 questionnaires.

Interim Analysis

Interim analysis of all safety and efficacy data may be performed at any time deemed appropriate by the Sponsor. Data will be analyzed for internal informational purposes, reports, presentations, and manuscripts.

Study Management

Institutional Review Board and Informed Consent

Hope Biosciences is required to obtain IRB oversight of the research study. The IRB must be provided with Hope Biosciences-approved study protocol. Performance of the study may not begin until written evidence of IRB approval has been provided to Hope Biosciences. The

Allogeneic HB-adMSCs to provide immune support against COVID-19.

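### Exclusion 1 does not limit its contraception clause to women of childbearing potential, so it contradicts the stated population, and no pregnancy test is listed to back its pregnancy clause before the infusions

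*Protocol*

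**What the plan says.** Exclusion Criterion 1 in the protocol reads: "Women who are pregnant or lactating, or those who are not pregnant but do not take effective contraceptive measures". Neither the protocol nor the SAP limits the second half of that sentence by menopausal status or childbearing potential, and neither defines an effective contraceptive measure.

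Three other places in the protocol describe who is meant to be in the trial:

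- Inclusion Criterion 1 admits "Men, and women 18 years of age or older", with no upper age limit.
- The Investigational Plan defines high risk as a class that "includes subjects age 65 or older, as well as subjects in high exposure environments".
- The Analysis Population section names "Men, and women, age 65 or older OR high exposure risk individuals".

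Inclusion Criterion 2 then requires every participant to work in a high-risk or very high-risk exposure job.

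On testing, the Study Procedures section says that "Table 2 outlines the timing of procedures, and assessments to be performed throughout the study". The Clinical Laboratory Parameters section gives a list headed "Laboratory tests to be performed during the study". Five infusions are planned, at Weeks 0, 2, 6, 10 and 14. On the product, the Risks section says: "The risks associated with this cellular product are currently unknown".

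**The concern.** There are two separate problems in one criterion.

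The first is wording. A woman past menopause is not pregnant and ordinarily has no reason to use contraception, so the criterion as written excludes her. Site staff must then either turn away women whom other sections of the protocol name as part of the population, or enrol them against a written exclusion. The Protocol Deviations section forbids knowing departures from the protocol without prior approval, apart from emergencies and similar protective reasons. The first course narrows the group to which the result applies. The second puts avoidable eligibility deviations on record.

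The second is verification. Pregnancy is the first-listed exclusion, yet the plan lists no objective test for it. An unrecognised pregnancy at Week 0 could pass the eligibility review, and the participant could be randomised and infused. No other section of the public protocol or SAP mentions pregnancy, so no later planned procedure is directed at finding one.

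**Working it through.** The plan states no figure on this point, so the check compares the text of one section with another and counts scheduled tests.

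**Step 1: does the contraception clause conflict with the population text?** Take a post-menopausal woman who works in a job that meets Inclusion Criterion 2 and uses no contraception.

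| Place in the protocol | Result for this woman |
|---|---|
| Inclusion Criterion 1 (18 or older, no upper limit) | admitted |
| Inclusion Criterion 2 (high-exposure occupation) | admitted, by assumption |
| Investigational Plan, definition of high risk | within the class, by occupation and, from 65, also by age |
| Analysis Population | within the population, by exposure and, from 65, also by age |
| Exclusion Criterion 1, contraception clause as written | excluded |

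The last row cannot be applied literally together with the intent of the others. The conflict does not require her to be 65 or older. It arises for any post-menopausal woman in an eligible job.

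**Step 2: is a pregnancy test listed anywhere?**

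| Place | Items | Pregnancy tests |
|---|---|---|
| Table 2, Schedule of Assessments | 21 procedure rows | 0 |
| Clinical Laboratory Parameters list | 8 (blood count with differential, chemistry, coagulation, CRP, IL-6, IL-10, TNF-alpha, rapid COVID-19 antibody) | 0 |
| Screening, infusion, follow-up and end-of-study procedures | text lists | 0 |
| SAP 8.2, Clinical Laboratory Analyses | biochemistry, haematology, coagulation; urine parameters mentioned | 0 |

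**Step 3: what does check the pregnancy clause?**

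- Table 2 labels screening as a phone call, up to 45 days ahead, and marks no sample there.
- Table 2 marks inclusion and exclusion review at screening and again at Week 0.
- From Week 0, medical history, concomitant medication and physical examination are marked at every visit. The Physical Examination section says the limited examination serves partly to confirm that the participant still qualifies.
- The assessment before each infusion is a morning telephone call about symptoms.

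The pregnancy clause is therefore checked by report, history and examination, and not by a test.

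**Step 4: can a test be added without a new visit?** Yes. Table 2 places blood sampling at Weeks 0, 6, 14 and 26. The infusion-visit text gives Weeks 0, 2, 6, 10, 14 and 26. The two disagree about Weeks 2 and 10 but agree on Week 0. Baseline assessments precede the first infusion, and randomisation takes place at baseline.

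**The case against.** The strongest reply on the wording is that a contraception requirement presupposes that conception is possible, so any sensible site would apply it only to women who can conceive. The population text itself suggests that the authors did not mean to bar older women. That is a fair account of intent, but it concedes that the written rule differs from the intended one, and eligibility is audited against what is written.

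A second reply is that the clash with women aged 65 or older is thinner than it looks. Inclusion Criterion 2 is occupational, so age alone makes nobody eligible, and the population text already departs from the operative criteria for that reason. This stands. It narrows the affected group to post-menopausal women in high-exposure jobs but does not remove the contradiction. The age table running to 100–109 years adds little, since it is a generic template whose printed total is 100 rather than 53.

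On testing, Table 2 may not be a complete record. The re-screening text mentions screening laboratory values, and the Risks section mentions a coagulation panel and pathogen testing at screening, none of which is marked in Table 2's screening column. The chemistry panel is not itemised, and the consent pages are not public. An unlisted pregnancy test therefore cannot be ruled out. What can be said is that none is listed where sites would look for it.

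Three stronger readings are tempting and are not supported:

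- **That the rule also bars sterilised women.** Effective contraceptive measures are undefined, and sterilisation can reasonably count as one.
- **That pregnancy status is never checked.** Eligibility is reviewed at Week 0, and history and examination recur at every visit from then on. Only a test is missing.
- **That a number of lost participants or undetected pregnancies can be stated.** The documents give no sex distribution, menopausal status or pregnancy rate. Any such figure would consist of outside assumptions, and candidates who are turned away can be replaced under the cap of 53.

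**Conclusion.** The point holds on both parts, as an eligibility and safety-verification defect. As written, Exclusion Criterion 1 bars post-menopausal women in eligible jobs who use no contraception, contrary to Inclusion Criterion 1 and the Analysis Population text. The count of listed pregnancy tests is 0 of 21 Table 2 rows and 0 of 8 laboratory tests, so none is scheduled before any of the five infusions.

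The first part rests on reading the criterion literally. The second rests on the public text being what sites follow for scheduled tests. The number of women affected cannot be derived from the documents. Neither part changes the primary analysis, the error rate or the sample size. The change is still worth making, because the criterion misstates who is eligible and the first-listed exclusion lacks objective verification for a product of unknown risk.

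**What to change.** 1. Reconcile Exclusion Criterion 1 with Inclusion Criterion 1 and the Analysis Population text by limiting its contraception clause to women of childbearing potential. The sponsor should define that term and state what counts as an effective contraceptive measure, which would also settle the position of sterilised women.
2. Add a pregnancy-test row to Table 2, and the same entry to the Clinical Laboratory Parameters list, for women of childbearing potential at Week 0, with the result available before randomisation. It can be run on the blood already drawn at that visit. If a laboratory result would arrive too late, a rapid urine test serves.
3. State whether the test is repeated at later infusion visits. That is for the sponsor to decide.

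The cost is one reworded criterion with its definitions, one table row, one list entry and a small charge per test. At one test per randomised woman of childbearing potential, the Week 0 total cannot exceed 53, apart from tests on women who are then found ineligible. No extra visit or participant is needed, and the analysis is unchanged.
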